4.2 Design Diagram

This is a Phase 3, double-blind, randomized, multicenter study of higher versus standard adalimumab dosing regimens for induction and maintenance therapy in subjects with moderately to severely active UC (Mayo Score of 6 to 12 points with an endoscopy

subscore of 2 or 3, confirmed by a central reader). For all Mayo Score evaluations throughout the study, the stool frequency and the rectal bleeding subscores will be calculated based on entries recorded in daily electronic patient diaries.

The study was designed to enroll 840 subjects (504 subjects in the higher induction dose regimen and 336 subjects in the standard induction dose regimen) at approximately 125 sites for the main study and 100 subjects (60 in the higher induction dose regimen and 40 in the standard induction dose regimen) at 21 sites for Japan Sub-Study to meet scientific and regulatory objectives without enrolling an undue number of subjects in alignment with ethical considerations. Therefore, if the target number of subjects has been enrolled, there is a possibility that additional subjects in screening will not be enrolled.

This study will include:

An up to 21 days Screening Period

[figure not shown]
An 8-Week Double-Blind Induction Study

A 44-Week Double-Blind Maintenance Study

A 70-Day Follow-Up Period

During both the Induction Study and the Maintenance Study, visit week designations will represent weeks since first adalimumab dose in the Induction Study. Week 0 (Baseline) will reflect the date of first adalimumab dosing in the Induction Study. Week 8 will represent the final assessment in the Induction Study and the beginning of the Maintenance Study. Week 52 will represent the final assessment in the Maintenance Study (representing 44 weeks of maintenance treatment in the Maintenance Study). A subject's participation in the study is anticipated to be up to 65 weeks. There is a \pm 3 day window for all study visits. An effort will be made to bring subjects back to their original scheduled visit (calculated from Baseline) if they are out of the visit window.

A schematic of the study design is presented in [Figure 1](#).

Figure 1. Study Schematic

Screening Period

The Screening Period begins at the Screening Visit and continues through to Baseline Visit (Week 0). Screening Assessments will include medical history, physical examination, chest x-ray, endoscopy (colonoscopy or flexible sigmoidoscopy), electrocardiogram (ECG), diary review and laboratory results including pregnancy testing, all of which will be reviewed by the study site to confirm selection criteria are met prior to enrolling the subject.

8-Week Double-Blind Induction Study

Subjects who meet all of the inclusion criteria and none of the exclusion criteria will be enrolled into the 8-Week Induction Study. The main study and the Japan sub-study will each allow enrollment of up to 25% of subjects with previous infliximab exposure.

[figure not shown]
Subjects will be randomized via interactive response system (IRT) at Baseline (Week 0) to one of 2 double-blinded adalimumab induction regimens (higher dose or standard dose) in a 3:2 ratio. Use of the 3:2 randomization scheme allows for collection of additional

safety data with the higher induction dose regimen. The randomization will be stratified by:

Previous infliximab use, and
Baseline corticosteroid use.

The higher induction dose regimen of 160 mg at Weeks 0, 1, 2, and 3, followed by 40 mg at Weeks 4 and 6 leads to a total adalimumab dose over 8 weeks that is approximately twice that of the standard induction regimen (720 mg versus 320 mg) as shown in Figure 2 below.

Figure 2. 8-Week Double-Blind Induction Study

Subjects will return to the study site at scheduled visits and complete study procedures for each visit.

At Week 4, all subjects who were on oral corticosteroids at Baseline will have their corticosteroid dose tapered according to the proposed tapering schedule outlined in the protocol. If the Investigator feels that the steroid taper is not advisable for a particular subject at Week 4, the SDP should be consulted for evaluation and approval.

44-Week Double-Blind Maintenance Study

At the conclusion of the 8-Week Double-Blind Induction Study, subjects will return to the study site and will be re-randomized via IRT into the 44-Week Double-Blind Maintenance Study of the main study to one of three treatment groups in a 2:2:1 ratio:

Adalimumab 40 mg eow.

Adalimumab 40 mg every week (ew).

Adalimumab Therapeutic Drug Monitoring (TDM) regimen (exploratory).

The TDM regimen in the maintenance period will not be applied to the Japan sub-study because of logistical challenges in obtaining adalimumab serum concentration results within the time period specified in the main study. At the conclusion of the 8-Week Double-Blind Induction Study, subjects will return to the study site and will be re-randomized using the same stratification variables as the main study via IRT into the 44-Week Double-Blind Maintenance Study to one of two treatment groups in a 1:1 ratio with the same stratification from the main study:

Adalimumab 40 mg eow

Adalimumab 40 mg every week (ew)

Throughout the study, subjects will only be allowed to change the dosage of UC-specific concomitant medications as specified below:

At Week 4, all subjects who are taking oral corticosteroids from Baseline will have their corticosteroid therapy tapered according to the proposed tapering schedule specified in the Protocol. If the Investigator feels that the steroid taper is not advisable for a particular subject at Week 4, the SDP should be consulted for evaluation and approval.

Subjects taking corticosteroids at Baseline who have a loss of satisfactory clinical response per the Investigators judgment after the steroid taper has been initiated may have their corticosteroid dose increased per the Investigator's discretion during the study.
Subjects in whom the maximum equivalent steroid dose exceeds the dose used at Baseline will be censored for efficacy assessments from the point forward. These subjects will continue to be evaluated in the safety population.

70-Day Follow-Up/Premature Discontinuation

Subjects may discontinue adalimumab treatment at any time during study participation. Subjects who end study participation early will have a premature discontinuation (PD) Visit. All subjects will have a follow-up phone call approximately 70 days after the last administration of study drug to obtain information on any new or ongoing AEs. The 70 day follow-up phone call will not be required for any subject who initiates commercial adalimumab.

4.3 Sample Size

An additional 100 subjects has been determined as the proper sample size for the Japan Sub-Study based on the following rationale. Using the same assumptions as the main study with the following:

Remission rate for induction treatment at 8 weeks: 35% in the high dose group and 20% in the standard dose group

Remission rate for maintenance treatment at 52 weeks among Week 8 responders: 48% in the high dose group and 30% in the standard dose group

Overall response rate for induction treatment at Week 8: 50%

$\alpha = 5\%$, power = 95% for induction study

$\alpha = 5\%$, power = 90% for maintenance study

The precisions of point estimations of remission rates in Japanese population are included within the 95% CI of remission rates in integrated population will be within 20% with 100 subjects. With this sample size, the probability to show consistency between

Japanese population and integrated population will be greater than 80% using the method 2 shown in the "Basic principles on global clinical trials."

4.4 Final Analysis of Induction Japan Sub-Study

The final analysis of the primary endpoint, ranked secondary efficacy variables and additional efficacy variables for the Induction Study only as well as safety data collected from Baseline through double-blind Week 8 will be performed after the last subject in the ITT (Section 5.1 for definition) population completes the 8-week double-blind Induction Study of the Main Study and Japan Sub-Study. A database lock will be performed and any discrepant data will be clarified before the lock. The statistical methods for the analysis of the primary endpoint are outlined in Section 10.2. The statistical methods for the analyses of the ranked secondary efficacy endpoints are outlined in Section 10.3.

4.5 Derived, Defined and Transformed Variables

The following defined variables will be used:

Full Mayo Score

- Full Mayo Score is defined as the composite score of UC disease activity based on the subscores of stool frequency (0 – 3), rectal bleeding (0 – 3), physician's global assessment (0 – 3) and endoscopy (0 – 3). This score ranges from 0 – 12 points with higher scores representing more severe disease (also see Section 6.0 for the rules for calculation of rectal bleeding and stool frequency subscores).
- Clinical Response is defined as a decrease in Full Mayo Score of ≥ 3 points and $\geq 30\%$ from Baseline, PLUS a decrease in the rectal bleeding subscore [RBS] ≥ 1 or an absolute RBS ≤ 1 .
- Clinical Remission is defined as Full Mayo Score ≤ 2 with no subscore > 1 .

Partial Mayo Score

- Partial Mayo Score is defined as the composite score of UC disease activity based on the subscores of stool frequency, rectal bleeding, and physician's global assessment and DOES NOT include the endoscopy

subscore. This score ranges from 0 – 9 points also see Section 6.0 for the rules for calculation of rectal bleeding and stool frequency subscores.

- Clinical Response per Partial Mayo Score is defined as a decrease in Partial Mayo Score ≥ 2 points and $\geq 30\%$ from Baseline, PLUS a decrease in RBS ≥ 1 or an absolute RBS ≤ 1 .
- Clinical Remission per Partial Mayo Score is defined as Partial Mayo Score ≤ 2 , with no subscore > 1 .

Adapted Mayo Score

- Adapted Mayo Score is defined as Full Mayo Score minus the Physician's Global Assessment (PGA) subscore.
- Clinical Remission per Adapted Mayo Score is defined as an Adapted Mayo Score ≤ 2 , with stool frequency subscore ≤ 1 , RBS of 0, and endoscopic subscore ≤ 1 .
- Clinical Response per Adapted Mayo Score is defined as a decrease in the Adapted Mayo Score ≥ 2 points and $\geq 30\%$ from baseline, PLUS a decrease in RBS ≥ 1 or an absolute RBS ≤ 1 .

IBDQ Response

- IBDQ Response is defined as at least a 16 point increase from Baseline in total Inflammatory Bowel Disease Questionnaire (IBDQ) score.

Endoscopic Improvement

- Endoscopic Improvement is defined as endoscopy subscore of 0 or 1.

Endoscopic Remission

- Endoscopic Remission is defined as endoscopy subscore of 0.

5.0 Analysis Populations

5.1 Definition for Analysis Populations

The Japanese population is defined as all Japanese subjects who were randomized at Japanese sites. The following populations will be used for analyses in the Japan Sub-Study:

The integrated ITT (I-ITT) dataset includes all randomized subjects (at both Japanese sites and all other sites in the main study). The Japan ITT (J-ITT) dataset includes all Japanese subjects who were randomized at Japanese sites only and will be used for efficacy analyses of Japanese subjects separately from other subjects in the main study.

The integrated Safety set consists for Induction Study of all subjects (from both Japanese sites and those sites following the parent protocol) who received at least one dose of study medication. The Japan Safety set for Induction Study consists of all randomized Japanese subjects from Japanese sites who received at least one dose of study medication.

5.2 Variables Used for Stratification of Randomization

At Baseline, subjects will be randomized 3:2 to one of two double-blinded adalimumab induction dosing regimens (higher dose or standard dose) for the Induction Study. The randomization will be stratified by previous infliximab use and baseline corticosteroid use. The randomization schedules will be prepared separately for the main study and the Japan sub-study by the Statistics Department of AbbVie.

6.0 Analysis Conventions

Definition of Baseline

The baseline visit date is the date when the first dose of study drug was received during Induction Study and referred to as Day 1 or Week 0. The baseline value for a variable is defined as the last non-missing value before the first dose of study drug during Induction Study. When dosing times or observation times are not collected, it is assumed that observations obtained on the day of the first dose of study drug (Day 1) are prior to the first dose of study drug and therefore baseline values.

Definition of Final Observation

Final Observation in the 8-week double-blind Induction Study is defined as the last non-missing observation collected within 70 days following the last dose of study drug for subjects who are not re-randomized, and on or before the day of the first dose of study

drug in the 44-week double-blind Maintenance Study for subjects who entered the Maintenance Study. Of note, the efficacy, laboratory, and vital sign evaluations performed on the day of first dose of study drug in the double-blind Maintenance Study will be included in the efficacy and safety analyses for the Induction Study. AEs onset on the date of the first dose of the Maintenance Study will be attributed to the Maintenance Study.

Definition of Treatment Compliance

Compliance (%) is defined as the number of injections received divided by the number of injections planned (rounded to 0.1) during the subject's participation in the Induction Study.

Definition of Rx Days (Days Relative to the First Dose of Study Drug)

Rx Days are calculated for each time point of interest and provide a quantitative measure of days between an event and the first dose date. The Rx Day during the Induction Study is calculated as the event date minus the date of first dose of the Induction Study drug plus 1. The Rx Day will be a negative value when the time point of interest is prior to the date of first dose of study drug, and the Rx Day will be a positive value when the time point of interest is after the first dose date. By this calculation algorithm the first dose day is Rx Day 1, while the day prior to the date of first dose is defined as Rx Day –1 (there is no Rx Day 0). Rx days are used to map actual study visits to the protocol specified study visits during the Induction Study (Rx Day A), as defined below.

Definition of Analysis Windows

Since subjects do not always adhere to the study visit schedule, the following rules will be applied to assign actual visits to protocol-specified visits including early termination visits. For each study visit mentioned in the protocol, a nominal or target day along with a window around the target day will be selected to represent the corresponding visit. Windows will be selected in a non-overlapping fashion so that a date collected on the CRF does not correspond to multiple visit windows. Moreover, windows will not discard

any post-baseline measurement recorded on the CRF. If a subject had two or more actual visits in one visit window, the visit closest to the target will be used as the study visit for that window. If two visits are equidistant from the target, then the later visit will be used for reporting. If more than one assessment is collected on the same day, then the average of those assessments will be used in analyses.

Table 1. Visit Windows for Analysis of Efficacy Variables, Laboratory Parameters and Vital Signs (Induction Study)

Scheduled Week	Nominal Day	Time Window (Rx Day A Range)
Week 0 ^a	1	≤ 1
Week 1	8	2 – 11
Week 2	15	12 – 22
Week 4	29	23 – 43
Week 8 ^a	57	44 – 71 ^b

Rx Day A = date of visit – date of first study drug injection in the Induction Study + 1

a. hs-CRP and fecal calprotectin collections are scheduled at Screening/Week 0 and Week 8 per protocol.

b. Minimum of Day 71 or the date of the first injection in the Maintenance Study, if applicable.

Table 2. Visit Windows for Analysis of Endoscopy Variables (Induction Study)

Scheduled Week	Nominal Day	Time Window (Rx Day A Range)
Week 0	1	≤ 1
Week 8	57	2 – 71 ^a

Rx Day A = date of visit – date of first study drug injection in the Induction Study + 1

a. Minimum of Day 71 or the date of the first injection in the Maintenance Study, if applicable.

Table 3. Visit Windows for Analysis of IBDQ, SF-36 and WPAI (Induction Study)

Scheduled Week	Nominal Day	Time Window (Rx Day A Range)
Week 0 ^a	1	≤ 1
Week 2	15	2 – 22
Week 4	29	23 – 43
Week 8 ^a	57	44 – 71 ^b

Rx Day A = date of visit – date of first study drug injection in the Induction Period + 1

- a. SF-36 and WPAI collections are scheduled at Week 0 and Week 8 per protocol.
- b. Minimum of Day 71 or the date of the first injection in the Maintenance Study, if applicable.

Definition of Missing Data Imputation

The following imputation methods will be used to impute missing values in the efficacy analyses. In addition, an observed case analysis will be performed.

Non-Responder Imputation (NRI)

The NRI approach is used for binary efficacy variables. These variables can take values of 'Achieved' or 'Not Achieved,' or may be missing for any reason including discontinuation from study. According to the NRI imputation approach, all missing value will be considered as 'Not Achieved.' In addition, subjects who prematurely discontinue from the study drug will be considered as 'Not Achieved' for all subsequent visits after discontinuation.

Observed Case (OC)

The OC analysis will not impute values for missing evaluations, and thus a subject who does not have an evaluation on a scheduled visit will be excluded from the OC analysis for that visit. In addition, the OC analysis will not use values after premature discontinuation of study drug.

Mixed-Effect Model Repeated Measure (MMRM)

The repeated measure analysis will be conducted using mixed model including observed measurements at all visits. Data collected after premature discontinuation of study drug will be excluded from the analysis. The mixed model includes the categorical fixed effects of treatment, visit and treatment-by-visit interaction, stratification factors at randomization, and the continuous fixed covariates of baseline measurement. An unstructured variance covariance matrix will be used.

Last Observation Carried Forward (LOCF)

The LOCF rule will be used to impute for missing continuous and categorical efficacy data. Baseline and Pre-Baseline values will not be used to impute the missing Post-Baseline values. Missing values after Study Day 1 will be imputed using the latest non-missing value after Day 1 and prior to the missing value. If there are no non-missing values after Baseline, then the LOCF value will be missing. If a subject has missing values for a specific visit, the data will be imputed using LOCF only for the period which the subject started.

Rules for Calculation of Stool Frequency Subscore and Rectal Bleeding Subscore

The diary entries on the days the subjects take endoscopy preparation medications, the day of endoscopy procedure, and 2 days after endoscopy procedure will be excluded. For the calculation of the stool frequency subscore and the rectal bleeding subscore at each visit, the most recent 5 available diary days from up to 14 days preceding the visit will be used.

To calculate these subscores when fewer than 5 days of diary data are available in the previous 14 days, the average will be based on the most recent 4 days will be used if only 4 days are available, or the average will be based on the most recent 3 days will be used if only 3 days are available.

If the subject has fewer than 3 days of diary entries, the score for that subject at the visit will be considered missing, and the subject will be categorized as a non-responder (NRI) for any categorical endpoints relating to data for this visit.

Rounding to one decimal place will be applied to the calculation above for the subscores, Partial Mayo Score and Full Mayo Score.

The last day of the 5 days will be used to decide the actual visits that should be assigned to the Mayo Score and Partial Mayo Score data.

Rules for Efficacy Assessment Based on Concomitant Treatment

Subjects in whom the UC-related systemic or rectal corticosteroids that were not being taken at Baseline and are initiated during the study or who have dosages of these medications increased to greater than the dose taken at Baseline will be censored for efficacy assessments (i.e., will be considered non-responders for categorical endpoints and will have last non-missing values carried forward for non-categorical assessments) from that point through the end of the study. These subjects will continue to be evaluated in the safety population.

The equivalent steroid dose will be determined based on [Table 4](#):

Table 4. Equivalent Steroid Dose

Corticosteroid	Equivalent Dose (mg)
Cortisone	25
Hydrocortisone	20
Prednisone	5
Prednisolone	5
Triamcinolone	4.0
Methylprednisolone	4.0
Betamethasone	0.75
Dexamethasone	0.75
Budesonide	1
Beclomethasone	5

Definition of Medication Use at Baseline

Medications are considered to be used at Baseline if the medication start date is on or before the first study drug dose date and the medication end date is on or after the first study drug dose date. All medications with a start date after the first study drug dose date or an end date before the first dose date are excluded.

Treatment Interruption

If the study drug treatment interruption is longer than 60 days and treatment re-introduction is evaluated as not feasible, the subject will be considered as premature discontinuation from the study in all efficacy assessment after the last dose and all the aforementioned imputation rules apply.

Imputation of Missing Dates

For Baseline, efficacy, and safety parameters, if the day and/or month are missing, the following conventions will be used to impute the missing dates:

01 for missing start day

End of month for missing end day

January 1st for missing start month

December 31st for missing end month

7.0 Demographics, Baseline Characteristics, Medical History, and Previous/Concomitant Medications

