10.4 Additional Efficacy Analyses

Additional pre-specified endpoints in the Induction Study:

All-cause and UC-related hospitalization and surgery rates during Weeks 0 – 8.

Change from Baseline in histologic score at Week 8.

Proportion of subjects achieving clinical remission per Adapted Mayo Score at Week 8.

Proportion of subjects achieving clinical remission defined as Adapted Mayo score ≤ 2 with no subscore > 1 at Week 8.

Relationship between histologic subscores and endoscopic improvement (endoscopy subscore of 0 or 1) at Week 8.

Relationship between histologic scores and endoscopic subscore of 0 at Week 8.

Proportion of subjects achieving clinical remission per Partial Mayo score over time.
Proportion of subjects achieving clinical response per Partial Mayo score over time.
Proportion of subjects with SFS of 0, RBS of 0 and endoscopic subscore of 0 at Week 8
Proportion of subjects with SFS < 1 over time
Proportion of subjects with RBS of 0 over time
Change from Baseline in hs-CRP over time.
Change from Baseline in IBDQ total and domain score over time.
Proportion of subjects with IBDQ total score ≥ 170 over time.
Change from Baseline in Mayo score, Partial Mayo score, Adapted Mayo score and Mayo subscores over time.
Change from Baseline in laboratory and nutritional parameters (e.g., hemoglobin, hematocrit, albumin, total protein concentration, and weight).
Change from Baseline in subject-reported stool frequency (absolute values).
Change from Baseline in work productivity and impairment questionnaire (WPAI) scores over time.
Change from Baseline in SF-36 score over time.
Change from Baseline in fecal calprotectin over time.
Time to achievement of clinical remission (per Partial Mayo score)
Time to achievement of clinical response (per Partial Mayo score)
Change in presence of extraintestinal manifestations over time.

For categorical variables the difference in proportions of subjects between treatment groups will be analyzed similarly as the ranked secondary endpoints and the CMH based two-sided 95% confidence interval (CI) for the difference in the proportions between the treatment groups will be calculated for I-ITT and J-ITT analysis set.

For the continuous endpoints the difference in change from baseline between treatment groups over time will be analyzed using a Mixed-Effect Model Repeated Measure (MMRM) model including factors of treatment, visit, treatment-by-visit interaction,

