stratification variables and Baseline values. Parameter estimates with 95% confidence interval and *P* value will be provided.

NRI for missing data will be used for categorical endpoints. Mixed-Effect Model Repeated Measure (MMRM) model will be applied for the continuous endpoints, where applicable.

Events of hospitalization and surgery will be identified by blinded adjudication of the serious adverse events (SAEs). Subjects in the safety analysis set for the Induction will be included in the all-cause and UC-related hospitalization and surgery rates analyses during the Induction Study.

All-cause hospitalization is defined as SAEs resulting in admission to the hospital or prolongation of an existing hospitalization for any reason. UC-related hospitalizations are defined as hospital admissions or prolongation of an existing hospitalization due to AEs or complications that are related to UC and included the following categories: UC-related surgery, hospitalizations for nonsurgical UC-related events, such as UC-related flares, and hospitalizations related to the complications/extra-intestinal manifestations of UC.

Unadjusted incidence rates will be used to assess the risk of all-cause and UC-related hospitalization and surgery rates during Weeks 0 – 8. The difference between the two treatment groups will be determined using Chi-square test.

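### The MMRM gives baseline one slope for all visits; if correlation with baseline falls over time, last-visit estimates lose some precision and can be slightly biased, and a baseline-by-visit term would prevent this (minor)

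*SAP*

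**What the plan says.** Section 6.0 of each SAP defines the MMRM. The fixed effects are "effects of treatment, visit and treatment-by-visit interaction, stratification factors at randomization, and the continuous fixed covariates of baseline measurement", and for the residuals "An unstructured variance covariance matrix will be used". Data after premature discontinuation of study drug are left out.

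Section 10.4 of the Induction SAP restates the model for change from baseline as a "Mixed-Effect Model Repeated Measure (MMRM) model including factors of treatment, visit, treatment-by-visit interaction", followed by "stratification variables and Baseline values. Parameter estimates with 95% confidence interval". Section 10.4 of the Maintenance SAP names the MMRM as the main analysis for continuous endpoints and leaves its terms to section 6.0. No baseline-by-visit term appears anywhere.

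The visit-window tables in section 6.0 show which endpoints have more than one post-baseline visit:

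- **Induction:** Weeks 1, 2, 4 and 8 for general efficacy and laboratory variables, and Weeks 2, 4 and 8 for IBDQ. Others have Week 8 alone: "hs-CRP and fecal calprotectin collections are scheduled at Screening/Week 0 and Week 8 per protocol", and "SF-36 and WPAI collections are scheduled at Week 0 and Week 8 per protocol".
- **Maintenance:** 11 visits for general efficacy and laboratory variables, 7 for hs-CRP, 5 for fecal calprotectin and 4 for IBDQ. SF-36 and WPAI have Week 52 only.
- **Endoscopy:** one post-baseline window in each period, so Full Mayo has one as well.

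**The concern.** The model lets visit means, treatment effects and residual covariance vary freely by visit, but holds the relation to baseline constant. If a measurement near baseline tracks baseline more closely than one taken weeks later, the fitted slope is a compromise weighted toward the early visits and is too steep at the last visit, which is usually the one of interest. Two things could follow:

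- The last-visit contrast is less precise than it need be.
- The MMRM relies on data being missing at random, and that needs a correct mean model. An unstructured covariance describes the residuals and does not repair a wrong slope, so dropout that depends on observed values can bias the last-visit means. That bias does not shrink with sample size.

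**Working it through.** The plan states no SD, correlation or dropout rate for any MMRM endpoint, so there is no figure to reproduce. Everything below rests on assumed values, shown as ranges.

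**Precision at Week 8, complete data**

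Take unit SDs, visits at Weeks 1, 2, 4 and 8, and correlation ρ_t with baseline at visit t. The true slope at visit t is then β_t = ρ_t. Let P be the inverse of the residual covariance given baseline.

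- Common slope in large samples: b = (1′Pβ)/(1′P1)
- Week 8 variance with the common slope: 1 − 2bρ₈ + b²
- Week 8 variance with a slope per visit: 1 − ρ₈²
- Unadjusted Week 8 value: 1
- Unadjusted change from baseline: 2 − 2ρ₈

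With baseline in the model, analysing change rather than the value only shifts the slope by 1, so the same formulas apply.

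Results with ρ₈ = 0.3, ρ_t falling in equal steps, and correlation between post-baseline visits of 0.75 per visit step (autoregressive). The slope-per-visit variance is 1 − 0.09 = 0.910 throughout.

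| Correlation with baseline | b | Common-slope variance | Excess over 0.910 |
|---|---|---|---|
| constant 0.3 | 0.300 | 1 − 0.180 + 0.090 = 0.910 | 0% |
| 0.5 to 0.3 | 0.414 | 1 − 0.248 + 0.171 = 0.923 | 1.4% |
| 0.6 to 0.3 | 0.488 | 1 − 0.293 + 0.238 = 0.945 | 3.9% |
| 0.7 to 0.3 | 0.580 | 1 − 0.348 + 0.336 = 0.988 | 8.6% |

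Across the other between-visit structures tried (autoregressive and constant), the ranges are 1-2%, 3-8% and 6-22%. They are not bounds, because stronger correlation between visits widens them. In standard errors, 22% in variance is √1.22 = 1.10.

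**Against an unadjusted change score**

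For ρ₈ = 0.3 its variance is 2 − 0.6 = 1.40. Even at an excess of 22%, the common-slope variance is 0.910 × 1.22 = 1.11, which keeps (1.40 − 1.11)/(1.40 − 0.91) = 59% of the possible gain. In general 1 − 2bρ₈ + b² < 2 − 2ρ₈ whenever 2ρ₈ − 1 < b < 1, so the common slope loses to the plain change score only if b exceeds 1 or falls below 2ρ₈ − 1.

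**Maintenance**

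Baseline is the pre-induction value and the first visit is Week 10, so the correlation may already be low and fairly flat. The excess is below 1% for 0.4 falling to 0.3, and 4-14% for 0.7 falling to 0.3.

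**Bias under dropout**

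Both models were fitted by maximum likelihood to large simulated data sets (60,000 per arm in one set, 80,000 subjects in another), with dropout depending on observed values except where stated. Biases at the last visit are in SD units.

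| Correlation with baseline | Dropout by arm | Arm mean(s) | Treatment difference |
|---|---|---|---|
| 0.7 per visit step (0.70, 0.49, 0.34, 0.24) | 21% in both | about +0.055 in both | −0.001 |
| same | 26-27% vs 9% | 0.05-0.07 in one arm | 0.04-0.06 |
| same | 9% vs 6% | about 0.015 | about 0 |
| 0.7 to 0.3 | 24% in both | +0.07 to +0.08 | not recorded |
| 0.7 to 0.3 | 24% vs 9% | not recorded | −0.067 (by-visit slope: +0.004) |
| 0.6 to 0.3 | 24% vs 9% | not recorded | −0.052 (by-visit slope: −0.010) |

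With constant correlation, or dropout completely at random, there was no bias beyond simulation noise.

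**The case against.** A single baseline main effect is a legitimate specification, and several limits on the point stand.

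- **No loss is certain.** A reader might infer that the model always over-adjusts at the last visit and gives up most or all of the benefit of adjusting. The documents give no correlations. With constant correlation nothing is lost, and with a mild fall the loss is 1-2%.
- **The benchmark matters.** A reader might also infer that the model does worse than no adjustment. Against the raw Week 8 value (variance 1), that can happen when the fall is steep. For example, 0.7 to 0.25 with 0.75 per visit step gives 1.044. But the plan analyses change from baseline, whose unadjusted variance there is 1.50, and the common slope remains well below it.
- **Arm-mean bias is mostly not effect bias.** It largely cancels in the treatment difference unless dropout differs clearly by arm.
- **The reach is limited.** Full Mayo, SF-36 and WPAI in both periods, and hs-CRP and fecal calprotectin in induction, have one post-baseline visit, where a common slope and a visit-specific slope are the same thing. The primary and ranked endpoints are binary and use CMH with non-responder imputation. The Induction SAP treats its tests as exploratory, and the additional endpoints carry no multiplicity control in either SAP.
- **The Japan-only maintenance set is small.** At the planned 50% response rate it holds about 100 × 0.50 = 50 Week 8 responders. An 11-visit unstructured covariance already has 11 × 12/2 = 66 parameters, and the fix adds 10 slopes.

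These points lower the priority. They do not make the constraint useful: it gains almost nothing if it is true and costs precision, and possibly bias, if it is false.

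**Conclusion.** The point holds as a conditional one of minor priority. Both SAPs fix one baseline slope across visits. If correlation with baseline falls over time, the Week 8 contrast has a variance larger by about 1-2%, 3-8% or 6-22% for falls to 0.3 from 0.5, 0.6 or 0.7, and by 0% if there is no fall. It still improves on an unadjusted change score. With falling correlation and dropout driven by observed values, arm means may be biased by roughly 0.05-0.08 SD. The treatment difference may be biased by about 0.04-0.07 SD, but only when dropout differs clearly between arms (about 24-27% against 9% in the cases run).

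All of these sizes rest on assumed correlations and dropout rates. They apply to Partial Mayo and the diary-based subscores, IBDQ and laboratory values, and in maintenance also to hs-CRP and fecal calprotectin. The documents do not support a claim that any primary or ranked result would change.

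**What to change.** Add the baseline-by-visit interaction to the MMRM fixed effects in section 6.0 of both SAPs and in the restated list in section 10.4 of the Induction SAP. Leave all other terms and the unstructured covariance as they are.

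The cost is one model term and no new data. Extra parameters equal the number of post-baseline visits minus one:

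- **Induction:** 3 for general efficacy and laboratory variables, 2 for IBDQ.
- **Maintenance:** 10 for general efficacy and laboratory variables, 6 for hs-CRP, 4 for fecal calprotectin and 3 for IBDQ.

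This is negligible in the integrated sets (840 + 100 = 940 subjects planned at randomization) and a small loss of degrees of freedom in the Japan-only sets.
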